3.7. Treatment Assignment & Blinding

At the Baseline visit, all eligible subjects will be randomized via the IXRS to one of the treatment arms. The Investigator or his/her delegate will contact the IXRS after confirming that the subject fulfills all the inclusion/exclusion criteria. The IXRS will prompt the user to randomize the subject. The subject identifier number will be used to link the subject to a treatment arm and a unique medication number for the bottles of study drug to be dispensed to the subject.

Randomization will be stratified based on the following factors that may influence the incidence and severity of RTIs and the response to treatment:

1. Age \geq 85
2. Age \geq 65 and $<$ 85 years with a medical history of asthma
3. Clinical Frailty Scale score \geq 4

Therefore, the 6 randomization strata are as follows:

- Age \geq 85 and Clinical Frailty Scale score \geq 4
- Age \geq 85 and Clinical Frailty Scale score $<$ 4
- Age \geq 65 and $<$ 85 years with a medical history of asthma and Clinical Frailty Scale score \geq 4
- Age \geq 65 and $<$ 85 years with a medical history of asthma and Clinical Frailty Scale score $<$ 4

This document is confidential.

- Age ≥ 65 and <85 years with no medical history of asthma and Clinical Frailty Scale score ≥ 4
- Age ≥ 65 and <85 years with no medical history of asthma and Clinical Frailty Scale score < 4

The randomization scheme for subjects will be reviewed and approved by a member of the team responsible for Randomization schema.

This is a subject, Investigator and Sponsor-blinded study. Subjects, all study site staff, including Investigators and study nurses, will remain blinded until all subjects complete the Long-term Follow up Period (Study Week 48). The Sponsor will remain blinded to study treatment until all subjects complete the Short-term Follow-up Period (Study Week 20). The only exception will be in the DMC. The DMC manager, coordinator, and statistician will have access to unblinded data and perform all work in a restricted and secured project folder. The unblinded files will be transferred to the unblinded DMC members by the unblinded DMC coordinator.

3.8. Administration of Study Medication

RTB101 10 mg or matching placebo will be dispensed at the Baseline visit, Week 4, Week 8, and Week 12. Subjects will be instructed to take one dose daily in the morning. Subjects participating in the PK assessments (per the IXRS randomization) will be asked not to take study drug on the morning of scheduled clinical visits of Week 4 (or alternatively Week 6 in case of logistical need) and Week 12 as the subject will be administered study drug with a light meal at the study site.

3.9. Study Procedures and Flowchart

The study will be comprised of up to a 4-week Screening Period; a 16-week Primary Analysis Period (for evaluating efficacy and safety) during which time subjects meeting study eligibility criteria will be randomized 1:1 to receive RTB101 10 mg or matching placebo once daily through the Week 16 Visit; a 4-week Short-term Follow-up Period (for evaluating safety and efficacy through the Week 20 Visit); and a 28-week Long-term Follow-up Period (for evaluating safety through Week 48 by follow-up questionnaire). The Blinded Treatment Period has clinical visits every 2 weeks for the first 8 weeks, and every 4 weeks thereafter (for a total of 7 visits including the Baseline visit).

Respiratory illness symptoms will be captured in an eDiary that subjects will complete daily (in the evening) at home after the Baseline visit. The eDiary will ask the subject to record their experience with a set of predefined respiratory illness symptoms at their worst during the past 24 hours. The subjects record whether each symptom was absent, mild, moderate or severe. If the subject experiences any symptom on a typical day even though they are not sick, they are instructed to record the symptom as "Absent". The predefined symptoms include both respiratory symptoms (runny nose, sneezing, stuffy nose, sore throat, hoarseness, or cough) and general symptoms (headache, feverishness/chills, loss of appetite, body aches, or lack of energy).

The eDiary responses will be monitored by the Study Investigator or Study Coordinator. The Study Investigator or Study Coordinator at the site will contact subjects who miss completion of the daily eDiary questionnaires for >1 day and re-train the subject and explain the importance of completing the daily eDiary questionnaires.

Study sites will instruct subjects who report at least one respiratory symptom in 2 consecutive entries in their eDiary to come to the study site for evaluation, if possible, and for the collection of a nasopharyngeal swab. Subjects who are unable to come to the study site may also have the nasopharyngeal swab (and, if indicated, a sputum specimen and rapid influenza diagnostic test [RIDT]) obtained during a home visit by

This document is confidential.

trained personnel.

Details of assessments at each visit are provided in Table 6-1 of the protocol.

This document is confidential.

4. Endpoints

4.1. Primary Efficacy Endpoint

The primary endpoint is the percentage of subjects with CSRIs (with or without an associated laboratory confirmed pathogen) beginning at least 3 days after the start of study drug treatment through Week 16 as assessed by pre-specified clinical diagnostic criteria defined in 7.2.1 below.

4.2. Secondary Efficacy Endpoints

The secondary endpoints are:

- The percentage of subjects with 1 or more CSRIs associated with ≥ 1 laboratory-confirmed pathogen(s) beginning at least 3 days after the start of study drug treatment through Week 16 as assessed by pre-specified clinical diagnostic criteria, and respiratory pathogen PCR of nasopharyngeal swabs, sputum gram stain and culture, and/or Rapid Influenza Diagnostic Tests (RIDTs).
- The rate of CSRIs associated with specific laboratory-confirmed viruses (coronaviruses, hMPV, HRV/enterovirus, adenovirus, influenza A and B virus, parainfluenza viruses, and RSV) beginning at least 3 days after the start of study drug treatment through Week 16 as assessed by respiratory pathogen PCR of nasopharyngeal swabs, sputum gram stain and culture, and/or RIDTs.
- The rate of CSRI (with or without an associated laboratory-confirmed pathogen) beginning at least 3 days after the start of study drug treatment through Week 16 as assessed by pre-specified clinical diagnostic criteria.
- The rate of CSRIs associated with ≥ 1 laboratory-confirmed pathogen(s) beginning at least 3 days after the start of study drug treatment through Week 16 as assessed by pre-specified clinical diagnostic criteria and respiratory pathogen PCR of nasopharyngeal swabs, sputum gram stain and culture, and/or RIDTs.
- The time to alleviation of moderate and severe respiratory illness symptoms due to a CSRI beginning at least 3 days after the start of study drug treatment through Week 16.
- The percentage of subjects with severe symptoms due to CSRIs beginning at least 3 days after the start of study drug treatment through Week 16.
- Safety and tolerability will be assessed by report of AE/SAEs, physical exam and ECG findings, and safety laboratory values.

4.3. Exploratory Endpoints

The exploratory endpoints are:

- The rate of all laboratory-confirmed viral infections with or without symptoms beginning at least 3 days after the start of study drug treatment through Week 16 as assessed by respiratory pathogen PCR of nasopharyngeal swabs and/or RIDTs (obtained during episodes of clinically

This document is confidential.

symptomatic respiratory illnesses) and/or respiratory pathogen PCR of mid-turbinate swabs (obtained at scheduled clinical visits even in the absence of symptoms). The rate of all-cause hospitalizations through Week 16.

- Rate of hospitalizations associated with RTIs beginning at least 3 days after the start of study drug treatment through Week 16.
- The rate of all-cause Emergency Room (ER) visits through Week 16.
- Rate of Emergency Room (ER) visits associated with RTIs beginning at least 3 days after the start of study drug treatment through Week 16.
- The rate of all-cause urgent care clinic visits through Week 16.
- The rate of urgent care clinic visits for CSRI beginning at least 3 days after the start of study drug treatment through Week 16.
- The rate of all-cause admissions to skilled nursing facilities through Week 16.
- Hospitalization length of stay associated with RTIs beginning at least 3 days after the start of study drug treatment through Week 16.
- All-cause hospitalization length of stay through Week 16.
- The percentage of subjects with one or more CSRIs (with or without an associated laboratory pathogen) beginning at least 3 days after the start of study drug treatment through Week 20
- The percentage of subjects with 1 or more CSRIs associated with ≥ 1 laboratory-confirmed pathogen(s) beginning at least 3 days after the start of study drug treatment through Week 20 as assessed by pre-specified clinical diagnostic criteria and respiratory pathogen PCR of nasopharyngeal swabs, sputum gram stain and culture, and/or RIDTs.
- The change from Baseline in HRQoL as assessed by EQ-5D-5L scores during all clinically symptomatic respiratory illness episodes beginning at least 3 days after the start of study drug treatment through Week 16 and at Week 16.
- The percentage of subjects who are ≥ 85 years of age with one or more CSRIs beginning at least 3 days after the start of study drug treatment through Week 16.
- The percentage of subjects who are ≥ 85 years of age with one or more CSRIs associated with ≥ 1 laboratory-confirmed pathogen(s) beginning at least 3 days after the start of study drug treatment through Week 16.
- The percentage of subjects who have a medical history of asthma with one or more CSRIs beginning at least 3 days after the start of study drug treatment through Week 16.
- The percentage of subjects who have a medical history of asthma with one or more associated with ≥ 1 laboratory-confirmed pathogen(s) beginning at least 3 days after the start of study drug treatment through Week 16.

This document is confidential.

- The rate of clinically symptomatic respiratory illnesses beginning at least 3 days after the start of study drug treatment through Week 16 in subjects who are ≥ 85 years of age.
- The rate of clinically symptomatic respiratory illnesses associated with ≥ 1 laboratory-confirmed pathogen(s) beginning at least 3 days after the start of study drug treatment through Week 16 in subjects who are ≥ 85 years of age
- The rate of clinically symptomatic respiratory illnesses beginning at least 3 days after the start of study drug treatment through Week 16 in subjects with a medical history of asthma.
- The rate of clinically symptomatic respiratory illnesses associated with ≥ 1 laboratory-confirmed pathogen(s) beginning at least 3 days after the start of study drug treatment through Week 16 in subjects with a medical history of asthma..
- The rate of asthma exacerbations defined as deterioration of asthma symptoms that requires treatment with systemic steroids beginning at least 3 days after the start of study drug treatment through Week 16 in subjects with a medical history of asthma.
- The percentage of subjects with 1 or more asthma exacerbation defined as deterioration of asthma symptoms that requires treatment with systemic steroids beginning at least 3 days after the start of study drug treatment through Week 16 in subjects with a medical history of asthma
- The percentage of subjects with one or more UTIs reported as adverse events through Week 16.
- The rate of UTIs reported as adverse events through Week 16.
- Change from Baseline to Weeks 4 and 16 in biomarkers in whole blood and serum and potentially future pharmacogenomic analysis.

This document is confidential.

5. Analysis Sets

5.1. Screening / Randomized Sets

The Screening Set (SCR) will include all subjects, who provided informed consent, regardless of the subject's randomization and study treatment status in the study. Unless specified otherwise, this set will be used for summaries of subject disposition.

The Randomized Set (RS) will include all subjects randomized whether treated or not.

5.2. Safety Set

The Safety Set (SAF) will include all subjects who were administered any dose of any study drug. Subjects will be analyzed per the actual study treatment they received. The follow-up period will include the Week 20 visit which is 4 weeks after the end of the treatment period. The SAF will be used for all analyses and presentation of by-subject listings of all safety endpoints. Subjects will be analyzed according the actual treatment they received.

5.3. Full Analysis Set

The Full Analysis Set (FAS) will include all randomized subjects who received at least 1 dose of trial medication. Subjects will be analyzed according to randomized treatment. The FAS will be used for all analyses and presentation of by-subject listings of all efficacy endpoints.

5.4. Per Protocol Set

The Per Protocol Set (PP) will include all subjects who complete the 16-week treatment period, missed < 20% of doses, and had no major protocol deviations impacting efficacy data. Subjects will be analyzed per the treatment group to which they were randomized.

Protocol deviations will be classified and reviewed for subject inclusion in the PP during a Blind Data Review Meeting (BDRM) as described in Syneos SOP 3911.00 (Blind) Data Review and Definition of Analysis Sets, prior to unblinding. Criteria for exclusion from the PP will be included in BDRM Preparation Plan.

This document is confidential.

6. Protocol Deviations

Protocol deviations will be collected throughout the study in the Medidata Clinical Trial Management System (CTMS). Protocol deviations will be reviewed during a BDRM. Details of selection criteria and documentation to be provided for review will be described in the BDRM Preparation Plan.

This document is confidential.

7. General Aspects for Statistical Analysis

7.1. General Methods

All analyses and outputs will be produced using SAS® version 9.4 or later. Unless otherwise specified, efficacy and safety summaries will be presented for each treatment. All other summaries will be presented for each treatment and overall. Continuous variables will be summarized using the number of observations (n), mean, standard deviation (SD), median, minimum, and maximum. Categorical variables will be summarized using number of observations (n), frequency, and percentages of subjects.

All relevant subject data will be included in listings. All randomized subjects entered into the database will be included in subject data listings. All by visit summaries will use the nominal visit. Unscheduled visits will not be summarized but will be included in the listings.

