5.5.2. Discontinuation of Study Treatment

Premature discontinuation of study treatment for a subject occurs when study drug is permanently stopped earlier than the protocol planned duration, and can be initiated by either the subject, the Investigator, or the Sponsor.

Study treatment must be permanently discontinued under the following circumstances:

- Subject decision-subjects may choose to discontinue study drug treatment for any reason at any time.
- The Investigator believes that continuation of study treatment would negatively impact the safety of the subject or the risk/benefit ratio of trial participation. This includes any laboratory abnormalities that in the judgment of the Investigator, taking into consideration the subject's overall status, prevents the subjects from continuing participation in the study.
- Any protocol deviation that results in a significant risk to the subject's safety.
- Emergence of the following AEs:
 - Hypersensitivity reaction to study drug
 - Gastrointestinal SAE
 - Oral ulcers, stomatitis, or diarrhea that limits oral intake or is associated with dehydration or weight loss (>2% from Baseline weight) over two or more consecutive study visits
 - Cardiac SAE (including, but not limited to, MI and unstable angina)
 - Study drug-related non-infectious pneumonitis (see [Section 13.2](#) [Appendix 2])
- Subject whose treatment has been unblinded.

If premature discontinuation of study treatment occurs, Investigator must determine the primary reason for the subject's premature discontinuation of study treatment and record this information on the CRF. Subjects who permanently discontinue study drug due to an AE should return to the study site as soon as possible for an unscheduled visit to return all study drug for reconciliation and accountability and to have the following assessments: vital signs, complete physical exam, and blood and urine collection for safety labs. Subjects who discontinue treatment for reasons other than an AE should return all study drug for reconciliation and accountability at the next study visit. UNLESS subjects withdraw their consent (see [Section 5.5.3](#)), they should return for all remaining study visits (including completing the daily eDiary). If they fail to return for these assessments for unknown reasons, every effort (e.g., telephone, e-mail, certified letter) should be made to contact the subject as specified in [Section 5.5.4](#) (Lost to follow-up).

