6.8.4. Electrocardiogram (ECG)

ECGs will be collected in accordance with the schedule outlined in the Table of Assessments (Table 6-1). ECGs may be obtained at additional times when deemed clinically necessary.

ECGs must be reviewed by a qualified physician (the Investigator or qualified designee) at the study site. Subjects with acute ischemic changes and/or with a QTcF >480 msec on ECG at Screening or Baseline are excluded from study participation (see Section 4.2). In all cases, the Investigator must document in the source documents the clinical considerations (i.e., result was/was not clinically significant and/or medically relevant) in allowing or disallowing the subject to be enrolled in the study.

Clinically significant ECG changes from Baseline occurring during the study must be evaluated for criteria defining an AE and reported as such if the criteria are met. Any QTcF >500 msec or >60 msec QTcF change from a subject's Baseline ECG, or any other clinically significant abnormal ECG change from Baseline should be reported as an AE. Appropriate follow-up medical care should be provided to all subjects who develop clinically significant ECG changes during the study.

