6.8.5. Laboratory Evaluations

In the case where a laboratory assessment that is listed in the inclusion/exclusion criteria is outside of a **protocol-specified range** at Screening, the assessment may be repeated once prior to randomization for the purpose of inclusion and to rule out laboratory error. If the repeat value remains outside of protocol-specified ranges at the Baseline visit, the subject is excluded from the study.

In the case where a laboratory range is not specified by the protocol but is outside the reference range for the laboratory at Screening, a decision regarding whether the result is of clinical significance or not shall be made by the Investigator and shall be based, in part, upon the nature and degree of the observed abnormality. The assessment may be repeated once prior to randomization for the purpose of inclusion and to rule out laboratory error.

In all cases, the Investigator must document in the source documents, the clinical considerations (i.e., result was/was not clinically significant and/or medically relevant) in allowing or disallowing the subject to be enrolled in the study.

Clinically relevant deviations of laboratory test results occurring during or at completion of the study should be evaluated for criteria defining an AE and reported as such if the criteria are met. Repeated evaluations are mandatory until normalization of the result(s) or until the change is no

longer clinically relevant. In case of doubt, the Sponsor Medical Monitor or designee should be contacted.

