7.4. Visit Windows

Visit window will not be used in the summarization or analysis of data.

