10.6. ECG

A 12-lead ECG will be performed during the study at Screening, Baseline, Week 4, Week 8, Week 12, and Week 16.

Observed values at each visit and changes from Baseline to each post-baseline visit in ECG parameter will be summarized by visit and treatment group using descriptive statistics. A summary of abnormal results for QTc, QTcB, and QTcF. Abnormal values will be categorized as >450 msec, >480 msec, >500 msec, change from baseline >30 msec, and/or change from baseline >60 msec.

Listings will be provided for all ECG parameters and interpretive results.

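### Safety labs and vital signs taken when a subject stops drug for an adverse event, and clinically prompted ECGs, enter no numeric or threshold count by arm, because the SAP does not summarise unscheduled visits and plans no worst-value table

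*SAP*

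**What the plan says.** **Summary rule.** SAP 7.1: "All by visit summaries will use the nominal visit". The next sentence reads "Unscheduled visits will not be summarized but will be included in the listings", with no exception for safety data. SAP 7.4 adds: "Visit window will not be used in the summarization or analysis of data". An off-schedule value therefore cannot be assigned to a nearby scheduled visit.

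**Where off-schedule safety values arise.** Protocol 5.5.2: "Subjects who permanently discontinue study drug due to an AE should return to the study site as soon as possible for an unscheduled visit". Vital signs, a complete physical examination and safety labs are done there. Table 6-1 has no column for stopping treatment. Protocol 6.8.4: "ECGs may be obtained at additional times when deemed clinically necessary". At unscheduled respiratory-illness visits, vital signs are taken and labs may be drawn if clinically indicated (Protocol 3.1 and Table 6-1).

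**Planned safety outputs.** SAP 10.4 gives lab descriptives and shift tables by visit; values above 2x ULN or below 0.5x LLN are listed only. SAP 10.5 gives vital-sign summaries and shifts by visit. SAP 10.6: "Abnormal values will be categorized as >450 msec, >480 msec, >500 msec, change from baseline >30 msec, and/or change from baseline >60 msec"; the table index presents these categories by visit (Table 14.3.4.2.3). No output uses a subject's worst post-baseline value or counts subjects abnormal at any time.

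**Protocol intention.** Protocol 9.4.3.3 says the arms will be compared on how many subjects, and what percentage, have abnormal or clinically relevant abnormal lab values. SAP section 12 records no departure from this.

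**The concern.** Off-schedule safety values are mostly taken because something prompted them, so they are more likely to be abnormal than routine ones. If they stay out of the tables, any-time abnormality is understated, and more so in an arm with more AE discontinuations. A safety reader would want to know how many subjects per arm ever passed a given lab or QTc threshold. The planned tables cannot answer that. A listing shows the individual values but gives no denominator, percentage or count by arm.

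**Working it through.** No stated figure in the plan is in dispute. The main check sets the sections side by side; the arithmetic only gives scale.

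**1. Where each value goes**

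| Value | Collected at | Numeric or threshold summary by arm | Automatic AE route |
|---|---|---|---|
| Labs when stopping drug for an AE | Unscheduled visit (Protocol 5.5.2) | None | ALT, AST or bilirubin >3x ULN (Protocol 6.8.5.2) |
| Vital signs at the same visit | Unscheduled visit | None | None |
| Clinically prompted ECG | Additional time (Protocol 6.8.4) | None | QTcF >500 msec or change >60 msec (Protocol 6.8.4) |
| Illness-visit vital signs and labs | Unscheduled visit (Table 6-1) | None | Liver tests as in row 1 |

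Other lab abnormalities are AEs only if they cause signs or symptoms, need therapy or are judged clinically significant (Protocol 7.1). Other ECG changes need a judgement of clinical significance.

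**2. What falls between**

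These SAP categories have no automatic AE route: QTc >450 msec, QTc >480 msec, change >30 msec, labs >2x ULN other than liver tests >3x ULN, and labs <0.5x LLN. An ALT between 2x and 3x ULN is an example. For QTcF >500 msec the AE route exists, but an AE table by preferred term does not give the numeric category. The QTc table's >500 msec row therefore misses a case seen only on an off-schedule ECG.

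**3. Chance that a transient abnormality meets a scheduled visit**

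Assumptions (mine): onset uniform over days 0 to 112; duration D days; visits exactly on schedule, ignoring the ±5-day windows.

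Inputs from Table 6-1:
- Labs on days 14, 28, 42, 56, 84 and 112. Week 20, day 140, adds nothing for D up to 28.
- ECGs on days 28, 56, 84 and 112.

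Formula: share = (onset days lying within D days before a visit) / 112.

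| D (days) | Labs | ECG |
|---|---|---|
| 3 | 6×3/112 = 18/112 = 16% | 4×3/112 = 12/112 = 11% |
| 7 | 6×7/112 = 42/112 = 38% | 4×7/112 = 28/112 = 25% |
| 14 | 6×14/112 = 84/112 = 75% | 4×14/112 = 56/112 = 50% |
| 21 | (56+21+21)/112 = 98/112 = 88% | 4×21/112 = 84/112 = 75% |
| 28 | 100% | 100% |

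At D = 21 the two-weekly lab visits cover the first 56 days completely. Short abnormalities would often miss the scheduled visits; those lasting four weeks would not.

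**4. Subjects with an AE-discontinuation visit**

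The documents give no rate. If 2% to 8% per arm is assumed, 533×0.02 = 10.7 and 533×0.08 = 42.6, so about 11 to 43 subjects per arm. This counts subjects with such a visit, not abnormal values missed.

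**5. Illness visits by arm**

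Under the assumptions in Protocol 9.6, 533×0.282 = 150.3 placebo subjects and 533×0.197 = 105.0 RTB101 subjects would have a clinically symptomatic respiratory illness, a difference of about 45. The trigger for an illness visit (one respiratory symptom on two consecutive diary entries) is looser than the illness definition, so the number of visits could be higher.

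**The case against.** A reader might infer that these values never enter any comparison between arms. The documents do not support that. QTcF above 500 msec or a change above 60 msec, liver tests above 3x ULN and other clinically significant abnormalities must be reported as AEs, whatever visit finds them. SAP 10.3 tabulates AEs by arm, including those leading to drug discontinuation. Subjects who stop drug are also asked to attend the remaining scheduled visits, so persistent abnormalities can be seen there. This objection stands and limits the point. It does not remove it: the minimum data in Protocol 5.5.2 for subjects who stop early omit labs, vital signs and ECGs, and the categories in step 2 depend on judgement to become AEs.

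A reader might also take SAP 7.1 as barring unscheduled visits from every analysis. That cannot be meant, because SAP 9.4.1 uses nasopharyngeal swabs, which are largely taken at unscheduled illness visits. Nor is data monitoring affected: the QTcF trigger in Protocol 5.5.5 leads to its own unblinded review and does not depend on the SAP table.

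Three further limits are fair:
- The AE-discontinuation visit names no ECG, so the QTc point rests on Protocol 6.8.4 alone.
- Mandatory repeat labs (Protocol 6.8.5) are weak evidence. The triggering value may already sit at a scheduled visit, and repeats run towards normal.
- The protocol synopsis itself plans safety summaries by scheduled time point, and safety analysis is descriptive. By-visit tables are therefore legitimate, but Protocol 9.4.3.3 asks for more than they give.

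Finally, pooling every off-schedule value would add illness-time readings mainly on placebo if the drug works (step 5), which could mask a drug effect on safety values. That is a sound argument about how to build the fix.

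**Conclusion.** The gap is real but narrow. Under SAP 7.1, 7.4 and 10.4 to 10.6, labs and vital signs from AE-discontinuation visits and clinically prompted ECGs enter no numeric or threshold count by arm. The AE tables cover the most serious findings. What is lost is the per-arm count of worst or abnormal values, mainly below the AE thresholds or judged not clinically significant, together with possible undercounting in the >500 msec row of the QTc table. Protocol 9.4.3.3 is met only in part.

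The documents do not allow the loss to be sized. The 11 to 43 subjects per arm and the coincidence percentages rest on the stated assumptions, and neither is a count of missed abnormalities. No efficacy conclusion is affected. The SAP should be changed because the data are already collected and the omission concerns values taken when a problem was suspected.

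**What to change.** - **SAP 7.1:** keep by-visit summaries on nominal visits, and state that unscheduled on-study values are used in the any-time tables below.
- **SAP 10.4 to 10.6:** add, by arm, a per-subject shift from baseline to the worst post-baseline value (highest and lowest) for labs and vital signs. Add counts and percentages of subjects ever passing each lab threshold and each QTc category. Use scheduled and unscheduled on-study records, including AE-discontinuation visits.
- **Illness visits:** show these tables with and without values from respiratory-illness visits, because such visits are expected to be more frequent on placebo.
- **Vital-sign shift table:** reconcile Table 14.3.4.3.2, titled as a shift to the last value on study, with SAP 10.5, which describes a shift at every post-baseline visit.

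The cost is SAP wording and a few extra tables. Off-schedule testing will raise abnormality counts somewhat, possibly unequally by arm; the paired display makes the illness-visit part of that visible.
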